The PRECISe trial is a bi-national, quadruple-blinded, multicenter randomized controlled trial (RCT) assessing the superiority of high versus standard enteral protein provision in mechanically ventilated ICU patients. (2)

Randomization

A computer algorithm was used to generate the concealed, random allocation sequence. Patients were randomized in a 1:1 ratio, stratified per center, using block randomization with random permuted block sizes varying between 4 and 6.

Sample size

The sample size calculation was based on a published cross-sectional measurement of the EQ-5D-5L health utility score at 180 days following ICU admission, as longitudinal data were unavailable (3). A minimum difference of 0.06 points on the EQ-5D-5L health utility score was selected to represent the minimum clinically important between-group difference to be detected. (4)

Based on these data, the sample size for the PRECISe trial was calculated as follows: assuming a standard deviation (SD) of 0.3 at 180 days (3), considering a two-sided type I error rate α of 5% and a type II error rate β of 20% (yielding a statistical power of 80%), 392 participants per intervention group will be required to detect the minimum clinically important difference of 0.06 in the EQ-5D-5L health utility score. In line with other critical care trials, the sample size has been adjusted upwards for an estimated 5% loss to follow-up for the primary endpoint. (5) After this adjustment, the final sample size for the PRECISe trial was set at 824 participants.

During the preplanned interim safety analysis after inclusion of 50% of patients, it became apparent that mortality was higher than anticipated, resulting in a standard deviation of the EQ-5D-5L HUS that was larger than expected (0.38 vs 0.30). Since this potentially could reduce the power of the study, the DSMB advised to increase the sample size. By running a Monte Carlo simulation of the primary outcome analysis using raw longitudinal data of the actual study population at that time (n = 709), without unblinding, it was calculated that with the observed standard deviation, a sample size of 935 patients would be required to retain 80% power to detect the minimally important difference of 0.06, while correcting for the actual loss-to-follow-up rate of 9.4%.

Framework

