The progress of all patients through the trial will be displayed as part of the CONSORT flow diagram. The number of patients who did not receive the allocated intervention will be reported, including corresponding reasons. Number of patients for whom no endpoints could be collected due to early withdrawal, and reasons for withdrawal, will be reported per trial phase. Patients who died will receive a score of 0 for the primary outcome and will be included in the final analyses, as described in the EQ-5D-5L user guide provided by the EuroQol Research Foundation. (6)

Baseline patient characteristics

The baseline characteristics in Table 1 will be summarized per treatment arm.

Age	Sex	BMI
Type of admission	Admission diagnosis system	ICU admission due to COVID-19 infection
Sepsis	Acute kidney injury	Glasgow Coma Scale
History of diabetes mellitus	APACHE II score	APACHE IV score
SAPS II score	SOFA score	EQ-5D-5L health utility score
Charlson Comorbidity Index	Rockwood Frailty Score	NRS-2002 score

Table 1. Baseline characteristics of the PRECISe trial.

BMI, Body Mass Index; ICU, Intensive Care Unit; COVID-19, Coronavirus Disease 2019; APACHE, Acute physiology and chronic health evaluation; SAPS, Simplified Acute Physiology Score; SOFA, Sequential Organ Failure Assessment; EQ-5D-5L, Euro-QoL-5D-5-level; NRS-2002, Nutritional Risk Screening 2002.

Section 5. Analysis

The purpose of this Statistical Analysis Plan (SAP) is to provide a comprehensive and detailed description of the methods of data analyses proposed for the PRECISe trial. This SAP is based on the study protocol version 5.0 (the Netherlands) and 4.0 (Belgium). The SAP is written in concordance with the guideline for statistical analysis plans, formulated by Gamble et al. (7)

The SAP will define the analyses that will minimally be executed. Statistical analysis will be performed under the responsibility of the authors of the SAP, under the supervision of the trial statistician, while following the statistical principles as formulated in the International Council for Harmonisation (ICH) guideline. (8) This SAP is reviewed and approved by the Trial Steering Committee.

Outcome definitions

Primary outcome

The primary outcome is health-related quality of life, assessed by the overall difference in EQ-5D-5L health utility score between the intervention and control groups over three time points (30, 90, and 180 days after ICU admission), adjusted for baseline EQ-5D-5L.

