- Domain data EQ-5D-5L: scores of subdomains of EQ-5D-5L at 30, 90, and 180 days after admission, with higher scores indicating increased impairment.
- Return to work: number of patients who return to work, and number of days between ICU admission and return to work.

Outcomes regarding protocol adherence are discussed separately under "Adherence and protocol deviations".

Lastly, a health economic evaluation will be performed. Details of this analysis are discussed separately under "Additional analyses".

Unblinding

To mitigate the consequences of an accidental unblinding during the trial, 4 randomization labels (A, B, C, D), were used. Each study group was coded by two different labels. The trial will be unblinded in a stepwise manner. After database lock, it will be revealed which two labels, , each belong together to form one of the groups (i.e., either the high protein or the standard protein group), but it will not yet be revealed which group they actually belong to. Therefore, subsequent analysis of the endpoints will be performed blinded. Only after the analyses are finalized, it will be revealed which group of labels is the high protein group and which group is the standard protein group. This way, the analyses will be done in a blinded fashion, preventing bias.

Analysis methods

Primary outcome

The primary outcome will be analyzed using a linear mixed effects model with a 3-level structure, i.e., repeated measurements are clustered within participants and participants are clustered within centers. The fixed factors are treatment group, time, treatment group*time, and baseline EQ-5D-5L.

With respect to the random-effects, two models will be considered: a random intercepts model and a random intercepts and slope model. The model with the lowest Akaike Information Criterion (AIC) will be selected. Correlations between follow-up measurements will be modelled either using an autoregressive model of the first order (AR1) or left unstructured. Again, the AIC will be used to select the model with the best fit to the data.

Homoscedasticity of the residuals will be assessed using Levene's test and inspected using residual plots. Normality of the residuals will be assessed using QQ-plots. In case of violation of homoscedasticity, the model will be extended with a variance function; in case of violation of normality, the outcome will be transformed. If the assumption is still violated after transformation, we will apply a robust mixed-effects fit.

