The assumed missing data mechanism for all endpoints is missing at random (MAR), given the amount of baseline covariates and other outcome variables collected. Longitudinal endpoints will be analyzed using mixed-effects models. This approach is robust with regard to MAR provided that variables contributing to the mechanism are used as covariates in the model.

In practice, baseline or outcome covariates will be introduced to the model if more than 5% of outcome data are missing. The baseline covariates in Table 1 and other outcome variables will be tested and added to the model if they are associated with the outcome or with a missingness indicator in univariate analysis with a P-value of < 0.05.

Missing data in other outcome data (not longitudinally assessed) and baseline covariates will be imputed using multiple imputation with fully conditional specification, in case the rate of missing data is more than 5%.

As a sensitivity analysis, we will perform the analysis of the primary outcome without modelling the MAR mechanism to test the robustness of our assumption.

Additional analyses

Health economic evaluation

The main question for the economic evaluation is to assess whether high enteral protein provision is cost-effective compared to standard enteral protein provision. The economic evaluation will be performed from a health care perspective over 180 days from ICU admission.

To quantify health care costs, data regarding ICU and hospital resource use will be collected, using the Dutch (Zorginstituut Nederland) and Belgian (RIZIV) guidelines for cost calculation. (14, 15) The following variables will be collected to quantify the most important medical costs within and outside

the hospital incurred by ICU patients: duration of mechanical ventilation, ICU and hospital length of stay, ICU and hospital readmissions, days on renal replacement therapy, days on intravenous antibiotics, complications, and admission to and duration of stay in a rehabilitation center.

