Given the mixture distribution of the EQ-5D-5L (the component of zero and the component other than 0), we will specify separate priors per longitudinally assessed outcome. Consequently, we will specify a prior for the mean difference with an EQ-5D-5L other than 0 and a prior for the proportion of patients who have an EQ-5D-5L score of 0 (i.e., deceased patients). This longitudinal analysis will be performed with adjustment for center as a random effect. The results of the analyses for the components will be presented separately and as weighted averages.

Analysis of longitudinally assessed secondary outcomes

Secondary outcomes for which no prior evidence was available will be estimated under a weakly informative prior, in a model similar to the longitudinally assessed primary outcome, with adjustment for the random effect of center.

Analysis of outcomes at one given time point

Secondary binary outcomes, such as 60-day mortality, will be expressed in ORs and absolute risk differences (ARD). These binary outcomes will be analyzed in a binary mixed regression model (Bernoulli distribution) with an adjustment for the random center effect. Priors for these binary outcomes are presented on the log OR scale in Table 1. Other secondary continuous outcomes, such as the duration of mechanical ventilation, will be reported in mean differences (MD) for the specific units of that endpoint. Finally, the abovementioned mixture distribution (the component of zero, and the component other than 0) will be used for the EQ-5D-5L assessment at the cross-sectional time points, and separate priors will be formulated, similar to the primary outcome assessment.

Handling of missing data

As the missingness of data is assumed to be missing at random (MAR), the linear mixed effects model will be appropriate to handle missing data.

Model settings and diagnostics

The models for our analysis will be implemented in *JAGS* using Markov Chain Monte Carlo (MCMC) algorithms, through the *R2jags* package (20, 21). Assessment of model convergence will be performed for key model parameters via potential scale reduction factors (Rhat) effective sample size (ESS), and other diagnostics such as density and trace plots. Model fit will be assessed in relative terms through the deviance information criterion (DIC and other criteria alike), and in absolute terms using posterior prediction checks (PPCs).

(Serious) Adverse events

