Appendix 5. Trial termination characteristics

Variable	Definition	Type of data
Rehabilitation center	Admission to rehabilitation center during follow-up period	Binary,
admission	and duration of stay in days	continuous
Return to work	Return to work (if applicable) and date of work resumption	Binary, date
Death	Survival status and date of death (if applicable)	Binary, date
Early trial termination	Reason for early trial termination, e.g., due to death or proxy or patient consent withdrawal, and date of early termination	Nominal, date
Unblinding	Occurrence of unblinding during trial participation	Binary

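### The primary model's missing-at-random assumption takes no account of vital status, so scores implied for patients known to be alive are pulled toward the zeros given to the dead

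*SAP*

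**What the plan says.** - **Deaths** (SAP Section 4, Trial Populations, Withdrawal/follow-up): "Patients who died will receive a score of 0 for the primary outcome and will be included in the final analyses".
- **Primary model** (Section 5, Analysis methods, Primary outcome): "The fixed factors are treatment group, time, treatment group*time, and baseline EQ-5D-5L", with random effects for participants and centres. Vital status is not listed.
- **Missing data** (Section 5): "Longitudinal endpoints will be analyzed using mixed-effects models. This approach is robust with regard to MAR", provided the variables behind the missingness are included as covariates. The rule for including them is that "baseline or outcome covariates will be introduced to the model if more than 5% of outcome data are missing". The candidates are the Table 1 baseline variables and further outcome variables, admitted on a univariate P-value below 0.05 against the outcome or a missingness indicator. The only missing-data sensitivity analysis of the primary outcome leaves that modelling out.
- **Data collected** (Appendix 5): "Survival status and date of death (if applicable". Consent withdrawal by patient or proxy is given as a reason for early termination. The SAP does not say whether vital status is obtained afterwards.
- **Scale of the problem** (Section 2, Sample size): loss to follow-up was 9.4%, and the SD rose from the planned 0.30 to 0.38 because mortality was higher than expected.
- **Bayesian analysis** (Section 5): "Given the mixture distribution of the EQ-5D-5L (the component of zero and the component other than 0" is recognised there and modelled in two parts, but only for that secondary analysis.

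**The concern.** A known death always has a score, so a missing score belongs to someone not known to be dead. For a patient known to be alive at the visit, the data already show that the missing value is not the death score. The model cannot use this. It implies a value from everyone with the same arm, visit and baseline, including the dead. If the patient has a score at another visit the pull is only partial; with no follow-up score it is full.

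The result is that deaths carry too much weight in both arms. Three consequences could reach the primary comparison:

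- unequal loss between arms could create a difference where none exists;
- an effect on survivors' utility would be diluted;
- an effect on mortality would be exaggerated.

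**Working it through.** **1. The plan's own figure.** n per arm = 2(1.960 + 0.842)² × 0.30²/0.06² = 392.4, against 392 stated. Then 784 × 1.05 = 823.2, against 824 stated. Neither is in dispute. The revised 935 comes from a simulation on trial data and cannot be re-run. Taken from the SAP below: loss of 9.4%, SD of 0.38, and a target of 0.06 at 80% power, which implies SE = 0.06/2.80 = 0.0214.

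**2. Assumptions.** The SAP gives no mortality (p), survivor mean (m), survivor SD (s) or loss by arm. With deaths at 0, SD² = (1−p)s² + p(1−p)m².

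| p | m | s | overall SD |
|---|---|---|---|
| 0.30 | 0.60 | 0.30 | 0.372 |
| 0.30 | 0.65 | 0.28 | 0.379 |
| 0.40 | 0.60 | 0.30 | 0.375 |
| 0.40 | 0.65 | 0.28 | 0.385 |
| 0.40 | 0.70 | 0.28–0.30 | 0.406–0.414 |

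The first four rows fit 0.38. The last does not and is not used.

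**3. Arm means.** Let q be the share lost, all survivors with no follow-up score. The model mean is m(1−p−q)/(1−q) and the true mean is m(1−p), so the shortfall is m·p·q/(1−q). With q = 0.094, q/(1−q) = 0.1038. The shortfall is 0.0187 and 0.0202 at p = 0.30 (m = 0.60, 0.65), and 0.0249 and 0.0270 at p = 0.40. A large-sample simulation of the three-visit model (unstructured covariance, no centre level) gave 0.012–0.017 at p = 0.30.

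**4. Contrast with no true effect.** If loss, mortality and survivor scores are alike, the shortfalls cancel. As an illustration, take losses of 6.4% and 12.4% (average 9.4%). The closed form is m·p·(0.124/0.876 − 0.064/0.936) = m·p × 0.0732: 0.0132 and 0.0143 at p = 0.30, 0.0176 and 0.0190 at p = 0.40. In simulation (model estimate minus full-data estimate, absolute value):

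| pattern of loss | p = 0.30 | p = 0.40 |
|---|---|---|
| lost patients miss every visit | 0.0117 | 0.0156 |
| progressive dropout | 0.0084 | 0.0110 |
| independent misses per visit | 0.0114 | 0.0153 |

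A further set of simulations widened the range to 0.006–0.017. With SE 0.0214, a bias of 0.006 gives a two-sided error of about 6%, 0.008 about 6.6%, 0.016 just under 12%, and 0.017 just over 12%.

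**5. Equal loss, real effect.**

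- *Survivor benefit only:* the closed-form ratio (1−p−q)/[(1−q)(1−p)] is 0.956 at p = 0.30 and 0.931 at p = 0.40, so dilution is 4–7% if every visit is missed. In simulation at p = 0.30, 0.0586 became 0.0563–0.0569, or about 3–4%.
- *Mortality benefit only (35% versus 30%):* in simulation about 0.0285 became 0.0303–0.0315, an inflation of 6–11%. In closed form, losing the same share of all patients gives 1/(1−0.094) = 1.104.

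**6. Mortality as a covariate.** In the same 35% versus 30% setting, adding death as a fixed covariate turned 0.0285 into about 0.000.

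**7. Survivors-only imputation.** With deaths held at 0 and missing survivors imputed from survivors, the full-data difference was recovered to within 0.0003.

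**The case against.** The strongest reply is that the SAP claims robustness only conditionally. Its 5% trigger will very probably be met at 9.4% loss, so the bare four-term model is unlikely to be the one relied on. That is true, but it does not rescue the analysis. Baseline covariates may predict death but do not record it. Mortality is among the SAP's outcome variables, so the rule neither requires nor excludes it; if it came in, the model would condition on part of the outcome and remove any effect acting through death (step 6). The sensitivity analysis drops the added covariates and so returns to the model at issue.

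Three stronger readings are tempting and are not supported:

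- *That deaths are always observed and only survivors are lost, so missingness at random is false throughout.* Patients who withdrew or were lost may have died later. For them, prediction from a mix of dead and alive is not obviously wrong. The criticism holds for patients known to be alive, and the SAP does not give their share of the 9.4%.
- *That the trial has an inflated type I error.* The 6.4% versus 12.4% split is invented for illustration. Nothing in the SAP suggests unequal loss, and the trial is blinded. With arms alike, the 5% level stands.
- *That the bias is large.* The calculations treat everyone lost as a survivor, which is the least favourable case. With equal loss, dilution at p = 0.30 is about 0.002 against a target of 0.06.

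**Conclusion.** The point holds for patients known to be alive: the stated handling lets observed deaths lower their implied scores, although the information to prevent this is collected. On the assumptions in step 2, with all lost patients survivors, each arm mean is too low by up to about 0.02–0.03. Whether the treatment contrast is biased depends on differences between arms. With none it is unbiased. With the illustrative six-point difference in loss the spurious effect is about 0.006–0.017, with a two-sided error of about 6–12%. The upper end needs about 40% mortality and lost patients missing every visit; independent misses at the same rate come close. With equal loss, a survivor effect is diluted by about 3–4% (closed-form upper limit 4–7%) and a mortality effect is inflated by about 6–11%. This is a moderate, avoidable weakness in the primary analysis, and no evidence that its result will be wrong.

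**What to change.** Amend the Missing data section as follows.

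1. Keep known deaths at 0.
2. For patients known to be alive at a visit, multiply impute the missing EQ-5D-5L from patients alive at that visit, by arm, using baseline covariates and the other EQ-5D-5L visits.
3. State how vital status is obtained for withdrawn or lost patients. Where it stays unknown, impute vital status first, then the score, and vary that assumption in a sensitivity analysis.
4. Fit the stated primary model to each completed data set and pool with Rubin's rules.
5. Change the covariate rule so that mortality and other post-randomisation outcomes serve only in the imputation model and never as covariates in the primary model.

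The Priors text of the Bayesian section describes the trial's approach as complete-case with non-survivors included; align it with the amended section.

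The cost is SAP wording, a modest imputation programme, and an explicit assumption for patients of unknown vital status. Known-alive patients need no new data, and the primary model's terms and the scoring of deaths do not change.

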The health utility score is derived from the responses to the 5-item EQ-5D-5L questionnaire, which is converted into a 5-digit number and then weighted using country-specific value sets, resulting in the EQ-5D-5L health utility score. The health utility score ranges from -0.532 to 1.0, with a score of 0 indicating death, a score below 0 indicating a state worse than death, a higher score indicating better health, and a score of 1 indicating perfect health.

Secondary outcomes

Clinical outcomes

Overall survival up to 180 days after ICU admission, with the use of Kaplan–Meier plots and a Cox proportional-hazards model, after ensuring, with the Schoenfeld residuals method, that the proportional-hazards assumption was met.

Functional outcomes

The following outcomes are collected at 30, 90, and 180 days after ICU admission.

- Health-related quality of life assessed by the Short Form 36 (SF-36): overall score, physical component score (PCS), and mental component score (MCS). Overall score ranges from 0 to 100, with higher scores indicating better Health-related Quality of Life.
- Anxiety and depression, assessed by the Hospital Anxiety and Depression Scale (HADS): oddnumbered questions measure symptoms of anxiety, and even-numbered questions measure symptoms of depression. Overall score ranges from 0 to 42, with higher scores indicating worse symptoms of anxiety and depression.
- Pain intensity assessed by the EQ-5D-5L pain question: ranges from 1 to 5, with higher scores indicating a more severe perception of pain or discomfort.
- Self-reported health assessed by the EQ-5D-5L visual analogue scale (EQ-VAS): ranges from 0 to 100, with higher scores indicating better self-reported health.
- Post-traumatic stress assessed by the Impact of Event Scale-Revised (IES-R): ranges from 0 to
 88, with higher scores indicating worse symptoms of post-traumatic stress.
- Physical function assessed by 6-minute walk distance: total distance (meters) covered over a time of 6 minutes, standardized for sex and age.
- Muscle and nerve function assessed by Medical Research Council (MRC)-sum score: ranges from 0 to 60, with higher scores indicating better muscle and nerve function.
- Muscle and nerve function assessed by handgrip strength: measured using a hand dynamometer and expressed in kilograms, standardized for sex and age.

Tertiary outcomes

Clinical outcomes

- Hospital mortality: number of patients who died during index hospital admission.

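### The missing-data rule lets other trial outcomes, mortality included, enter the primary model as covariates, which changes the effect being estimated

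*SAP*

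**What the plan says.** The primary outcome (Section 5, Outcome definitions) is the overall difference in EQ-5D-5L utility over days 30, 90 and 180, "adjusted for baseline EQ-5D-5L". The model is fixed under Analysis methods: "The fixed factors are treatment group, time, treatment group*time, and baseline EQ-5D-5L". Under Withdrawal/follow-up, "Patients who died will receive a score of 0 for the primary outcome and will be included in the final analyses".

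The Missing data section then changes that model on a condition: "baseline or outcome covariates will be introduced to the model if more than 5% of outcome data are missing". Table 1 variables and "other outcome variables will be tested and added to the model if they are associated with the outcome or with a missingness indicator" in a univariate screen at P < 0.05. It closes with a sensitivity analysis: "we will perform the analysis of the primary outcome without modelling the MAR mechanism".

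The outcomes listed in the same section include overall survival, hospital and 30-, 60- and 90-day mortality, days alive and at home at day 90, and SF-36. They also include this one: "Domain data EQ-5D-5L: scores of subdomains of EQ-5D-5L at 30, 90, and 180 days after admission". On the primary score itself: "The health utility score is derived from the responses to the 5-item EQ-5D-5L questionnaire".

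**The concern.** Every one of these outcomes is measured after randomisation and can be affected by treatment. Putting such a variable beside treatment in the regression removes the part of the treatment effect that runs through it. It can also create a difference where the total effect is zero. Baseline covariates do neither in a linear model.

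The rule conflicts with the SAP's own definition. The primary model has one covariate besides treatment and time, and death is part of the outcome. Adjusting for death takes out of the comparison what the score of 0 was meant to put in. Elsewhere the SAP respects the distinction: under Subgroup analyses, comparisons by post-randomisation groups are labelled exploratory.

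The consequence spreads. The same section governs all longitudinal endpoints, and the subgroup analyses take over the model specification of the primary analysis. A gap between the augmented model and its sensitivity analysis would be read as a comment on missing at random (MAR), although it mainly reflects conditioning on mediators.

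**Working it through.** **The plan's own figures.** With SD 0.30, difference 0.06, two-sided 5% and 80% power: 2 × (1.960 + 0.842)² × 0.30² / 0.06² = 392.4 per group, against 392 stated. Then 784 × 1.05 = 823.2, against 824. The design figures are not in dispute.

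**1. Is the rule triggered?** Sample size reports 9.4% actual loss to follow-up. The SAP does not say whether the 5% counts patients or visit values. As a share of visit values, 9.4% of patients lost gives:
- all lost before day 30: 9.4% × 3/3 = 9.4%
- evenly over the three intervals: 9.4% × 2/3 = 6.3%
- all lost after day 90: 9.4% × 1/3 = 3.1%

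The trigger is likely but not certain.

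**2. Would mortality pass the screen?** For mortality m, survivor mean μ and survivor SD s, with deaths at 0, the overall SD is √[m(1−m)μ² + (1−m)s²] and the correlation of death with the score is √[m(1−m)] × μ / SD. With m = 0.30, μ = 0.70 and s = 0.25 (assumed), the SD is 0.383 and the correlation 0.838 in absolute value. With 935 × 0.906 = 847 evaluable patients, t is about 45. Over m = 0.2 to 0.4 and μ = 0.6 to 0.7, the correlation is 0.73 to 0.87 and t about 31 to 51. Death passes.

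**3. What does adjustment for death remove?** With mortality p₀ (control) and p₁ (high protein) and survivor gain d, the effect at a visit is

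(1 − p₁) × d + (p₀ − p₁) × μ.

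Adjusting for death leaves roughly the first term.

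Assumed inputs, not in the SAP: control mortality 28/33/35% at days 30/90/180; survivor mean 0.55/0.66/0.72, SD 0.25. The overall SDs are then 0.33/0.37/0.40, against the SAP's 0.38. The mortality effect uses the SAP's literature-based prior for 60-day mortality (log OR mean −0.02, SD 0.09), applied here at all three visits. Its 95% range is −0.02 ± 1.96 × 0.09 = −0.196 to +0.156.

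| Log OR | Mean of (p₀ − p₁) × μ | 0.060 minus that | Simulated, 90-day mortality added |
|---|---|---|---|
| −0.02 | 0.003 | 0.057 | 0.057 |
| −0.196 | 0.026 | 0.034 | 0.034 |
| +0.156 | −0.022 | 0.082 | 0.084 |

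**4. Other outcomes as covariates**, same true 0.060, log OR −0.02, by simulation (random-intercept model, equal-weight mean of the three visit effects, centre omitted):
- days alive and at home (mean 50, SD 22, 0 if dead by day 90, correlation 0.4 with utility): 0.037; 0.048 to 0.024 for correlation 0.2 to 0.6
- SF-36-like score (survivor mean 50, SD 20, 0 for the dead, correlation 0.75): 0.018; 0.040 to 0.011 for correlation 0.5 to 0.8

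**5. Rejection rates** (2,000 replicates, N = 936, 9.4% lost at random):

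| Scenario | As planned | With mortality | With days at home | With SF-36-like score |
|---|---|---|---|---|
| True 0.060, log OR −0.02, any rejection | 70% | over 99% | 76% | 77% |
| Total effect 0, log OR +0.156, benefit declared | 2.8% | 46% | 10% | 10% |

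In the second row the survivor gain is set to cancel the deaths: mean survival under high protein is 0.645, so d = 0.0224 / 0.645 = 0.035. A plain regression on each patient's mean score gives 42 to 43% with mortality added.

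**6. Does the remedy work?** Loss of 9.4% of day-30 survivors was made to depend on the day-30 SF-36-like score. Complete data gave 0.060, the model under Analysis methods 0.061, imputation with that score as auxiliary 0.060, and the score as covariate 0.018. With the dependence differing by arm, the figures were 0.062, 0.060, 0.062 and 0.018.

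**The case against.** The strongest reply is that this is the widest reading. The stated purpose is to include variables that contribute to missingness, and a sensible team would not enter EQ-5D-5L items, which are absent whenever the score is absent. That is fair about intent, but the text sets no limit, and association with the outcome alone is enough for entry.

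That the augmented model is the primary one is inferred. The SAP does not say so outright, but calling the version without it a sensitivity analysis leaves little other reading. The intended estimate would still be reported, though under the wrong label.

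Several points on size stand:
- The trigger may not be met if visit values are counted and loss is late.
- The simulated planned model has 70% power, while the SAP's own simulation gives 80% at 935 patients, so the rejection rates are illustrations and not trial figures.
- The 46% is a tail case with exact cancellation. At the prior mean with zero total effect, rejection with mortality added is 5.7%, close to nominal. Averaged over the prior, again with exact cancellation, it is 18% against 6% as planned.
- In the lead case mortality moves the estimate by only 0.003. The larger shifts need assumed distributions and, for SF-36, a value after death that the SAP does not give.
- Some outcomes, such as ventilation days or ICU stay, are recorded without a follow-up visit and could inform missingness. That argues for using them as auxiliary variables, not as covariates.

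**Conclusion.** The rule is wrong as written and must be corrected. Followed literally, it replaces the all-patient difference, deaths scored 0, with a difference adjusted for survival or later function, and gives that the primary label.

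The main harm is the changed target, not lost power: with little mortality effect, adding mortality raises the rejection rate. Under the assumed inputs a true 0.060 becomes 0.034 to 0.084 with mortality added across the prior's 95% range, and 0.037 or 0.018 with days at home or an SF-36-like score. A total effect of zero can be declared a benefit.

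These sizes rest on assumed mortality, survivor utilities and correlations, and on one covariate being added at a time. That post-randomisation covariates change what is estimated does not depend on them.

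**What to change.** In the Missing data section:

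1. Remove outcome covariates from both sentences of the rule, so that only pre-randomisation (Table 1) variables can enter the primary and longitudinal secondary models.
2. State whether the 5% counts patients or visit values, and that deaths, scored 0, are not missing.
3. Name the primary model. The one under Analysis methods fits the outcome definition as it stands; the version with screened Table 1 covariates would then be the sensitivity analysis. The reverse is acceptable if stated, since baseline covariates leave the target unchanged.
4. If other outcomes are wanted to support MAR, use them only as auxiliary variables when multiply imputing survivors' missing values. Keep deaths at 0 and fit the unchanged analysis model.

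The cost is a few sentences. Step 4 is optional and needs some extra imputation code; multiple imputation with fully conditional specification is already planned for other variables. No new data are needed.
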